2.2 Rationale for the study design

This is a phase II, open label study to determine the efficacy and safety of treatment with BGJ398 in patients with a diagnosis of solid tumors or hematological malignancies that have been pre-identified (prior to study consent) to have FGFR genetic alterations and whose disease has progressed on or after standard treatment.

2.3 Rationale for dose and regimen selection

Patients enrolled in this study will receive 125 mg qd of BGJ398 on a 3 week on (21 day) /1 week off (7 day) schedule. This dose level and regimen is based on experiences from the [\[CBGJ398X2101\]](#) trial.

The MTD/RP2D from the CBGJ398X2101 study was identified as 125 mg administered once daily (qd) in continuous 28-day cycles. While dose levels of 100 mg qd and higher were tolerated by patients, the majority of the patients experienced reversible hyperphosphatemia,

which lead to study drug interruptions. An evaluation of the drug administration records for patients prior to receiving prophylactic phosphate-lowering therapy, indicated that the median time until first dose interruption was approximately 23 days and the median duration of interruption was 7 days. This observation led to the introduction of an expansion arm in the ongoing CBGJ398X2101 study to evaluate the administration of 125 mg qd on a 3 weeks on (21 days) / 1 week off (7 days) schedule in 28 -day cycles. To date, the majority of patients enrolled in this arm have completed their first cycle of therapy without hyperphosphatemia - induced dose interruptions, while maintaining anti-tumor activity.

The selection of the starting dose follows the ICH S9 guidelines for choosing a starting dose for a first-in-human trial conducted in patients with cancer, and is shown in [Table 6-2](#). It will be dosed on a flat scale and not adjusted by weight or body surface area.

3 Objectives and endpoints

Objectives and related endpoints are described in [Table 3-1](#) below.

Table 3-1 Objectives and related endpoints

Objective	Endpoint	Analysis
Primary: 
• To assess clinical benefit associated with BGJ398 treatment based on local investigator assessment.• For patients with solid tumors the assessment criteria will be RECIST 1.1 and will include responses of CR or PR or SD. For hematologic tumors other appropriate hematological response criteria will apply and are included in the appendices• For patients with TIO diagnosis without measureable/evaluable disease, the assessment criteria will be the tumor associated changes of metabolic parameters (plasma level of FGF23 < or =180 RU/mL; and inorganic phosphorous, calcium, and 1-25-dihydroxy vitamin D greater than the LLN (- 20%); and without requirement of supplementation therapy for at least the preceding cycle of the 16 week assessment.)	
• Clinical benefit rate (e.g. defined as CR or PR or SD \geq 16 weeks for solid tumors) at week 16. For hematologic tumors, other appropriate hematological response criteria will apply and are included in the appendices.• For patients with TIO diagnosis without measureable/evaluable disease, the following criteria will be the assessment at 16 weeks:
• the tumor associated changes of metabolic parameters: plasma level of FGF23 < or =180 RU/mL; and inorganic phosphorous, calcium, and 1-25-dihydroxy vitamin D greater than the LLN (- 20%); and• without requirement of supplementation therapy for at least the preceding cycle of the 16 week assessment.	Refer to Section 10.4 .
Key secondary: 
• To assess Overall Response (OR) of Partial Response (PR) or greater based on local investigator assessment.• For patients with solid tumors the assessment criteria will be RECIST 1.1 and will include responses of CR and/or PR. For hematologic tumors other appropriate hematological response criteria will apply and are included in the appendices.	
• Overall response rate (PR or greater)	Refer to Section 10.5.1 .

Objective	Endpoint	Analysis

Other secondary:
 
• To assess Progression-Free Survival (PFS) based on local investigator assessment per RECIST 1.1 or other appropriate hematological response criteria• To assess Overall Survival (OS)• To assess Duration of Response (DOR) based on local investigator assessment per RECIST 1.1 or other appropriate hematological response criteria• To assess safety and tolerability	
• Time from the date of first dose to the date of first documented disease progression or relapse or death due to any cause• Time from the date of first dose to the date of death due to any cause• Time from the first documented response to the date first documented disease progression or relapse or death due to any cause• Incidence of adverse events (AEs), serious adverse events (SAEs), changes from baseline in vital signs, laboratory test results(hematology, biochemistry), ECG, and cardiac imaging will be assessed by the Common Terminology Criteria for Adverse Events (CTCAE), v4.03	
Refer to Section 10.5.2.
 
Refer to Section 10.5.2.
 
Refer to Section 10.5.2.
 
Refer to Section 10.5.3.

4 Study design

[figure not shown]
4.1 Description of study design

This is a phase II, open label study to determine the efficacy and safety of treatment with BGJ398 in patients with a diagnosis of solid tumors or hematological malignancies that have been pre-identified (prior to study consent) to have FGFR genetic alterations and whose disease has progressed on or after standard treatment.

This study is intended for patients who have already had genomic profiling of their tumors in a CLIA certified laboratory and have already been pre-identified to have a tumor with a FGFR genetic alteration. Eligibility is based on FGFR genetic alteration status as assessed in the local, CLIA certified laboratory. The results of this testing must be known prior to signing the ICF and before formal screening begins. Laboratory results must be 'unambiguous' or 'unequivocal'. Results that state 'ambiguous' or 'equivocal' imply low probability that genetic deregulation is truly present and an important driver of patient's tumor. Once the patient has been identified, treating physicians who are qualified investigators may contact Novartis to consider enrollment in this study. For the purpose of this study, genomic profiling is not considered part of screening. Informed consent must be signed before any screening activities take place. Once eligibility criteria are met, the patient will initiate therapy with BGJ398 single-agent. The patient may not receive any additional anti-cancer therapy during treatment with BGJ398.

A schematic representation of the study start-up design is shown in [Figure 4-1](#).

Figure 4-1 Study start-up design

4.1.1 Treatment phase

Patients will continue to receive study treatment until disease progression (assessed by investigator per RECIST 1.1 or appropriate hematologic response criteria or for patients with TIO diagnosis the recurrence or progression of disease or recurrence of abnormal metabolic parameters), unacceptable toxicity, death or discontinuation from study treatment for any other reason (e.g., withdrawal of consent, start of a new anti-neoplastic therapy or at the discretion of the investigator), otherwise known as End of Treatment. Patients with TIO diagnosis that progress per RECIST but per investigator's assessment are receiving clinical benefit from treatment may remain on study upon approval from Novartis. Patients with TIO diagnosis that do not receive metabolic benefit by week 16 should discontinue unless approval from Novartis. All patients who discontinue from study treatment due to disease progression must have their progression clearly documented.

Disease assessments (per RECIST 1.1 or appropriate hematological response criteria) will be performed every 8 weeks (± 4 days) after first dose of study drug (Day 1 of every odd cycle), until disease progression or end of treatment, whichever occurs first. Upon implementation of this amendment, the frequency of disease assessment will be reduced and evaluations should be every 16 weeks after the first 16 weeks on treatment. Scans will be assessed locally by the investigator.

4.1.2 Follow-up phase

After discontinuation of treatment, patients, regardless of reason for treatment discontinuation, will be followed for safety for 30 days after the last dose.

All patients will be followed for survival status every 3 months for 2 years after the last patient has enrolled in the study, regardless of treatment discontinuation reason (except if consent is withdrawn or patient is lost to follow-up). If the primary efficacy endpoint is not met, Novartis may discontinue survival follow-up for this study.

For details on required assessments, please refer to [Table 7-1](#).

4.2 Definition of end of the study

End of study is defined as the time when the last patient completes survival follow-up as described in [Section 7.1.4.3](#), or when the last patient on study has died, been lost to follow up or withdraws consent, or when the study is terminated early, whichever occurs first.

The analysis of study data will be based on all patients' data up to the time when all patients have had the opportunity to complete at least 4 cycles (or 16 weeks) of treatment or discontinued the study. This will be the cut-off point for the primary clinical study report (CSR). Additional data for patients continuing to receive study treatment past the data cutoff

date for the primary CSR will be reported once all patients have discontinued treatment or been lost to follow-up. It will be reported in an addendum to the CSR, as appropriate.

At the time of CSR data cut-off, if patients are ongoing after 16 weeks on treatment and benefitting, they will continue to receive treatment, every effort will be made to continue provision of study treatment outside this study through an alternative setting to patients who in the opinion of the investigator are still deriving clinical benefit and the Novartis therapy is not commercially available and reimbursable.

4.3 Early study termination

The study can be terminated at any time for any reason by Novartis. Should this be necessary, the patient should be seen as soon as possible for an end of treatment (EOT) visit and the assessments for EOT should be performed as described in [Section 7](#) for a prematurely withdrawn patient. The investigator may be informed of additional procedures to be followed in order to ensure that adequate consideration is given to the protection of the patient's interests. The investigator will be responsible for informing the Institutional Review Board (IRB) and/or Ethics Committee (EC) of the early termination of the trial.

5 Population

5.1 Patient population

The study population will consist of 70- 120 adult patients with a diagnosis of a solid tumor or hematological malignancy that has been pre-identified as having FGFR genetic alterations. Patients with history/current evidence of tumor-induced osteomalacia (TIO) and FGF23-mediated hypophosphatemia with or without identification of an FGFR genetic alteration in the tumor will be allowed. Patients must have received at least one prior treatment for their recurrent, metastatic and/or locally advanced disease and have no remaining standard therapy options anticipated to result in a durable response. Patients must have progressive and measurable disease (per RECIST 1.1 or other appropriate hematological response assessment criteria) and be in need of treatment. For patients with TIO diagnosis, the presence of measurable or evaluable disease is not required provided there is evidence of FGF23-mediated hypophosphatemia (TIO patients will not be included in protocol amendment 3). This is a signal seeking study, attempting to identify additional patient populations who may benefit from treatment with single agent BGJ398.

Additional tumor types may be excluded during the course of the study at the discretion of Novartis. With Amendment 3, the study is re-opening for enrollment for the following six tumor types only: Head and Neck Squamous Cell Carcinoma, Bladder Cancer, Ovarian Cancer, Non-small cell lung carcinoma – Squamous, Glioblastoma with multiforme with FGFR 1-4 genetic alterations and Cholangiocarcinoma.

Patients must not have central nervous system (CNS) metastasis, leptomeningeal carcinomatosis, symptomatic cardiac disease, or impairment of gastrointestinal (GI) function. Patients must have archival tissue available for submission to allow for molecular testing related to pathway regulation. If tissue is not available or not of sufficient quantity the patient must be willing to undergo a fresh tumor biopsy to allow for this analysis. [REDACTED]

[REDACTED]

Note: An archival or fresh tumor sample may not be required if the patient has had their genomic profiling performed at a laboratory selected by Novartis and the patient has agreed to allow Novartis to use baseline molecular analysis results.

Enrollment is meant to encompass solid tumors and hematologic malignancies as having FGFR genetic alterations that may be inhibited by BGJ398 who otherwise meet all of the inclusion and none of the exclusion criteria. Amendment 3: no longer allows for patients with FGF ligand amplification or TIO diagnosis to be included. Though common for phase I studies, tissue-agnostic enrollment is unusual for phase II studies, which typically limit enrollment to one or a few well-defined tumors types. We expect that the study will enroll patients whose tumors have already been pre-identified to harbor FGFR genetic alterations such as Breast, Gastric, Esophageal, Colorectal, and Squamous Head and Neck cancers (the amendment 3 limits the tumor types from Head and Neck Squamous Cell Carcinoma, Bladder Cancer, Ovarian Cancer, Non-small cell lung carcinoma – Squamous, Glioblastoma with multiforme with FGFR 1-4 genetic alterations and Cholangiocarcinoma.). The total number of patients to be enrolled per tumor type will be based on an adaptive design. The adaptive design will be patient-sparing and allow the early closure of non-responding arms or arms where early success can be declared.

5.2 Inclusion criteria

Patients eligible for inclusion in this study have to meet **all** of the following criteria:

1. Patient has provided a signed study Informed Consent Form prior to any screening procedure
2. Patient is \geq 18 years of age on the day of consenting to the study.
3. Patient must have:
 - a. Confirmed diagnosis of (Head and Neck Squamous Cell Carcinoma, Bladder Cancer (Urothelial cell Carcinoma), Ovarian Cancer, Non-small cell lung carcinoma – Squamous, Glioblastoma multiforme and Cholangiocarcinoma are the only tumor types allowed) and is in need of treatment because of radiologic progression or relapse. Additional tumor types may be excluded during the course of the study at the discretion of Novartis. Note: Urothelial cell carcinoma, Cholangiocarcinoma, and Glioblastoma multiforme with FGFR 1-4 genetic alterations are allowed without any prior approval.
 - b. [Note: as of Amendment 3, TIO patients will not be enrolled in the study] Clinical evidence of tumor-induced osteomalacia (TIO) associated with FGF23-mediated hypophosphatemia with or without identification of an FGFR genetic alteration, with:
 - Advanced or inoperable malignancy
 - or tumors with contraindication to surgical resection (an elevated FGF23 level at baseline must be demonstrated)
 - or tumors not amenable to cure by surgical excision (documented by investigator)

- or tumor-induced osteomalacia diagnosis without the presence of measurable or evaluable disease

NOTE: Patients with a diagnosis of TIO without a pre-identified tumor genetic alteration may be included on a case by case basis upon prior approval by Novartis

4. Patient is in need of treatment because of progression or relapse defined as:
 - radiological progression for solid tumor and lymphoma
 - for hematologic malignancies, measureable progression or relapse by appropriate criteria (see appendices)
5. Patient must have been pre-identified as having a tumor with any FGFR genetic alteration [such as mutation, amplification, fusion, translocation of FGF receptors 1 – 4]. The qualifying genetic alteration must be assessed and reported by a CLIA-certified laboratory. (The FGF alteration must be in combination with a mutation or fusion in FGFR.)
6. Patient must have archival tissue available for submission to allow for molecular testing related to pathway regulation. If the tissue is not available or is insufficient, the patient must be willing to undergo a fresh tumor biopsy to allow for this analysis. The sample must be submitted prior to first study dose unless agreed upon between Novartis and the investigator. See [Section 7.2.4.2.1](#).
7. Patient must have received at least one prior treatment for recurrent, metastatic and /or locally advanced disease and for whom no standard therapy options are anticipated to result in a durable remission.
8. Recovery from adverse events of previous systemic anti-cancer therapies to baseline or grade 1, except for:
 - a. Alopecia
 - b. Stable neuropathy of \leq grade 2 due to prior cancer therapy
9. [Note: as of Amendment 3 **Diffuse large B cell lymphoma** patients will not be enrolled in the study] **Diffuse large B cell lymphoma only:** Patient has received or is ineligible for autologous or allogeneic stem cell transplant. This does not apply to patients with Mantle cell lymphoma or follicular lymphoma
10. Patients must have measurable disease as per appropriate guidelines:[as of Amendment 3 **Lymphoma, Symptomatic Multiple Myeloma, Leukemia and TIO** patients will not be enrolled in the study]
 - a. **Solid Tumors:** by RECIST 1.1 ([Appendix A](#))
 - b. **Lymphoma:** Patient has at least one measurable nodal lesion (≥ 2 cm) according to Cheson criteria ([Cheson 2007](#)). In case where the patient has no measurable nodal lesions ≥ 2 cm in the long axis at screening, then the patient must have at least one measurable extra-nodal lesion ([Appendix B](#))
 - c. **Symptomatic Multiple Myeloma:** by International Myeloma Working Group (IMWG)
 - Serum M-component of ≥ 1 gm/dL
 - Urine M-component of ≥ 200 mg/24 h

- Patients with plasmacytoma must have a definite increase in the size; a definite increase is defined as a 50% (and at least 1 cm) increase as measured serially by the sum of the products of the cross-diameters of the measurable lesion
- d. **Leukemia only:** Relapsed/refractory leukemia for which no standard therapy options are anticipated to result in a durable remission:
 - Acute myelogenous leukemia (AML) by World Health Organization (WHO) classification or acute lymphoblastic leukemia (ALL) relapsed or refractory to standard chemotherapy; unsuitable for standard chemotherapy or unwilling to undergo standard chemotherapy. Philadelphia chromosome (Ph) positive ALL eligible if failed prior tyrosine-kinase inhibitor therapy.
 - Age > 60 years with AML not candidates for or have refused standard chemotherapy, excluding patients with acute promyelocytic leukemia (APL) or with favorable cytogenetic abnormalities [inv16, t(8;21)].
 - For patients with Chronic Myeloid Leukemia (CML) only accelerated and blast phase CML will be allowed.
- e. **TIO diagnosis:** refer to inclusion 3b
- 11. Patient has an Eastern Cooperative Oncology Group (ECOG) performance status ≤ 1 ([Appendix N](#)).
- 12. Patient has a life expectancy of at least 16 weeks
- 13. All patients must have adequate bone marrow as described below:
 - a. Absolute Neutrophil Count (ANC) $\geq 1.0 \times 10^9/L$ (not applicable for leukemia patients)
 - b. Platelets (PLT) $\geq 75 \times 10^9/L$ (no platelet transfusion within past 14 days) (not applicable for leukemia patients)
 - c. Hemoglobin (Hgb) $\geq 9 \text{ g/dl}$ (not applicable for leukemia patients)
 - d. For Leukemia patients, peripheral blast counts $< 50,000 \text{ blasts/mm}^3$
 - e. International Normalized Ratio (INR) ≤ 1.5
 - f. For Leukemia patients, peripheral blast counts $< 50,000 \text{ blasts/mm}^3$
- 14. All patients must have adequate organ function defined as described below:
 - a. Potassium, calcium inorganic phosphorous and magnesium within normal limits (WNL). Supplementation is allowed to meet eligibility requirements
 - b. Serum creatinine $\leq 1.5 \times \text{ULN}$
 - c. Alanine aminotransferase (AST) and/or aspartate aminotransferase (ALT) $\leq 2.5 \times$ upper limit of normal range (ULN) or $\leq 5 \times \text{ULN}$ if liver metastases are present
 - d. Total serum bilirubin within normal range (or $\leq 1.5 \times \text{ULN}$)
 - e. Serum amylase and lipase \leq upper limit of normal (ULN)
 - f. Proteinuria \leq Grade 2 (dipstick or 24hrs urine analysis) (Not applicable for Urothelial cell carcinoma patients)

5.3 Exclusion criteria

Patients eligible for this study must not meet any of the following criteria:

1. Patients who have received prior treatment with BGJ398

2. Patients with a known hypersensitivity to BGJ398 or to its excipients
3. Patients with metastatic CNS tumors are excluded, unless the patient meets criteria a-e:
 - a. 4 weeks from prior therapy completion (including radiation and/or surgery)
 - b. Clinically stable with respect to the CNS tumor at the time of study entry
 - c. Not receiving steroid therapy
 - d. Not receiving anti-convulsive medications (that were started for brain metastases)
 - e. Patient with no leptomeningeal involvement
4. Current evidence of corneal or retinal disorder/ keratopathy including, but not limited to, bullous/band keratopathy, corneal abrasion, inflammation/ulceration, keratoconjunctivitis, confirmed by ophthalmologic examination
5. History and/or current evidence of significant tissue calcification including, but not limited to, the soft tissue, kidneys, intestine, myocardium and lung with the exception of calcified lymph nodes and asymptomatic coronary calcification
6. History and/or current evidence of endocrine alterations of calcium/phosphate homeostasis, e.g. parathyroid disorders, history of parathyroidectomy, tumor lysis, tumoral calcinosis etc.
7. Use of medications that increase serum levels of phosphorus and/or calcium. NOTE: Not applicable for TIO diagnosis
8. Consumption of grapefruit, grapefruit juice, pomegranates, star fruits, Seville oranges or products within 7 days prior to first dose
9. Use of medications that are known to prolong the QT interval and/or are associated with a risk of Torsades de Pointes (Tdp) 7 days prior to first dose
10. Use of amiodarone within 90 days prior to first dose
11. Current use of therapeutic doses of warfarin sodium or any other coumadin-derivative anticoagulants. Heparin and/or low molecular weight heparins are allowed.
12. Patients who are currently treated with drugs known to be strong inhibitors or inducers of isoenzyme CYP3A, or substrates of CYP3A4 whose treatment cannot be discontinued or switched to a different medication prior to starting study drug.
13. Patients with diarrhea \geq CTCAE grade 2
14. Patients with neuropathy \geq CTCAE grade 2 unrelated to prior cancer therapy, or $>$ grade 2 neuropathy for any other reason
15. Patients with acute or chronic pancreatitis.
16. Patients with external biliary drains.
17. Patients with impaired cardiac function or clinically significant cardiac diseases, including any of the following:
 - a. History (<6 months) or presence of serious uncontrolled ventricular arrhythmias or atrial fibrillation
 - b. Clinically significant resting bradycardia
 - c. LVEF $<$ 50% as determined by MUGA scan or ECHO
 - d. Any of the following within 6 months prior to starting study drug: myocardial infarction (MI), severe/unstable angina, coronary artery bypass graft (CABG),

congestive heart failure (CHF) requiring treatment, cerebrovascular accident (CVA), transient ischemic Attack (TIA), deep vein thrombosis, or pulmonary embolism

- e. Uncontrolled hypertension defined by a SBP \geq 160 mm Hg and/or DBP \geq 100 mm Hg, with or without anti-hypertensive medication(s). Initiation or adjustment of antihypertensive medication(s) is allowed prior to study entry.
 - f. QTcF $>$ 470 msec (for male and female) on screening ECGs
- 18. Patients with uncontrolled diabetes mellitus.
- 19. Patients with clinical evidence of active CNS leukemia
- 20. Patients who have received allogeneic stem cell transplant and/or have active graft-versus-host disease (GVHD)
- 21. Patients who have received autologous stem cell transplant within last 4 weeks
- 22. Impairment of GI function or GI disease that may significantly alter the absorption of BGJ398 (e.g. severe ulcerative diseases, uncontrolled nausea, vomiting, diarrhea, malabsorption syndrome, or small bowel resection)
- 23. Any other condition that would, in the Investigator's judgment, contraindicate patient's participation in the clinical study due to safety concerns or compliance with clinical study procedures, e.g. infection/inflammation, intestinal obstruction, unable to swallow oral medication, social/psychological complications
- 24. Patients who have been treated with any hematopoietic colony-stimulating growth factors (e.g., G-CSF, GM-CSF) \leq 2 weeks prior to starting study drug. Erythropoietin or darbepoetin therapy, if initiated at least 2 weeks prior to enrollment, may be continued. Restriction is not applicable for patients with Leukemia
- 25. Patient has received chemotherapy or anticancer therapy \leq 4 weeks (6 weeks for nitrosourea, monoclonal antibodies or mitomycin-C) prior to starting study drug or who have not recovered to a grade 1 from side effects of such therapy (except for alopecia and neuropathy). Patients with leukemia may receive therapy with hydroxyurea and/or steroids for the purpose of cytoreduction but must discontinue use prior to first dose of study drug.
- 26. Patients who have received the last administration of an anticancer targeted small molecule therapy (e.g. sunitinib, pazopanib, everolimus) \leq 2 weeks prior to starting study drug, or who have not recovered from the side effects of such therapy.
- 27. Patients not able to discontinue their current anti-cancer therapy prior to first dose of study drug.
- 28. Patients who have received radiotherapy \leq 4 weeks prior to starting the study drug or who have not recovered from radiotherapy-related toxicities (note: palliative radiotherapy for bone lesions \leq 2 weeks prior to starting study drug is allowed)
- 29. Patients who have undergone major surgery (e.g., intra-thoracic, intra-abdominal, intra-pelvic) \leq 2 weeks prior to starting study treatment or who have not recovered from side effects of such surgery.
- 30. Patients with previous or concurrent primary malignancy within 3 years prior to starting study treatment, with the exception of adequately treated basal cell carcinoma, squamous cell carcinoma or other non-melanomatous skin cancer, or in-situ carcinoma of the uterine cervix treated curatively and without evidence of recurrence.

31. Cirrhosis of the liver or known hepatitis B or C infection that is either acute or is considered chronic because the virus did not become undetectable:

- Hepatitis C Virus (HCV) infection: acute or chronic infection as depicted by a positive HCV RNA testing (note: in a patient with known anti-HCV but with a negative test for HCV RNA, re-testing for HCV RNA 4-6 months later is requested to confirm the resolution of HCV infection).
- Hepatitis B Virus (HBV) infection: acute infection (HBsAg+ with or without HBeAg+ or detectable serum HBV DNA), HBV carriers as evidence by ongoing presence of HBsAg and detectable serum HBV DNA levels.

32. Patients who have received investigational agents within $\leq 5t_{1/2}$ of the agent (or ≤ 4 weeks when half-life is unknown) prior to starting study drug.

33. Known diagnosis of human immunodeficiency virus (HIV) infection (HIV testing is not mandatory).

34. Patient has a history of non-compliance to medical regimen

35. Pregnant or nursing (lactating) women, where pregnancy is defined as the state of a female after conception and until the termination of gestation, confirmed by a positive hCG laboratory test

[figure not shown]
36. Women of child-bearing potential, defined as all women physiologically capable of becoming pregnant, unless they are using highly effective methods of contraception during dosing and for 3 months following the discontinuation of study treatment.

Highly effective contraception methods include:

- Total abstinence (when this is in line with the preferred and usual lifestyle of the subject). Periodic abstinence (e.g., calendar, ovulation, symptothermal, post-ovulation methods) and withdrawal are not acceptable methods of contraception
- Female sterilization (have had surgical bilateral oophorectomy with or without hysterectomy) or tubal ligation at least six weeks before taking study treatment. In case of oophorectomy alone, only when the reproductive status of the woman has been confirmed by follow up hormone level assessment
- Male sterilization (at least 6 months prior to screening). For female patients on the study the vasectomized male partner should be the sole partner for that patient.
- Combination of the following (a+b or a+c, or b+c):
 - Use of oral, injected or implanted hormonal methods of contraception or other forms of hormonal contraception that have comparable efficacy (failure rate <1%), for example hormone vaginal ring or transdermal hormone contraception
 - Placement of an intrauterine device (IUD) or intrauterine system (IUS)
 - Barrier methods of contraception: Condom or Occlusive cap (diaphragm or cervical/vault caps) with spermicidal foam/gel/film/cream/vaginal suppository

In case of use of oral contraception women should have been stable on the same oral contraception for a minimum of 3 months before taking study treatment.

Oral contraceptives (OC), injected or implanted hormonal methods are not allowed as the sole method of contraception because BGJ398 has not been characterized with respect to the potential to interfere with PK and/or the effectiveness of OCs.

Post-menopausal women are allowed to participate in this study. Women are considered post-menopausal and not of child bearing potential if they have had 12 months of natural (spontaneous) amenorrhea with an appropriate clinical profile (e.g. age appropriate, history of vasomotor symptoms) or have had surgical bilateral oophorectomy (with or without hysterectomy) or tubal ligation at least six weeks ago. In the case of oophorectomy alone, only when the reproductive status of the woman has been confirmed by follow up hormone level assessment, then she will be considered not of child bearing potential.

37. Sexually active males unless they use a condom during intercourse while taking drug and for 3 months after the last dose of the study drug and should not father a child in this period. A condom is required to be used also by vasectomized men in order to prevent delivery of the drug via seminal fluid.

6 Treatment

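### As printed, exclusion 28 admits palliative bone radiotherapy on Days -1 to -14 but bars it on Days -15 to -28

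*Protocol*

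**What the plan says.** Everything here is in Protocol Section 5.3, where meeting any one criterion excludes the patient.

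- **Exclusion 28, main clause:** excludes patients given radiotherapy ≤ "4 weeks prior to starting the study drug or who have not recovered from radiotherapy-related toxicities".
- **Exclusion 28, note:** in parentheses, palliative radiotherapy to bone ≤ "2 weeks prior to starting study drug is allowed". With its sign as it stands in the text, the line reads "bone lesions \leq 2 weeks prior to starting study drug is allowed". The code in that quote is the ≤ sign.
- **Exclusion 25:** opens "Patient has received chemotherapy or anticancer therapy" and sets 4 weeks (6 for nitrosoureas, monoclonal antibodies and mitomycin-C). It does not say whether radiotherapy or targeted small molecules are included.
- **Exclusion 26:** "Patients who have received the last administration of an anticancer targeted small molecule therapy (e.g. sunitinib, pazopanib, everolimus", and similar drugs, with a window of 2 weeks.

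No text states which criterion prevails where 25 overlaps 26 or 28. The SAP does not address the point.

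**The concern.** A washout rule normally becomes easier to meet as treatment recedes. This one runs the other way inside the 4-week period: irradiation last week is acceptable, irradiation three weeks ago is not.

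The criterion decides who may be dosed and when, and a site that sees the oddity has no formal way to correct it. Section 7.1.1.2 rules out waivers and Section 12 authorizes no deviations. One site may follow the words and another the presumed meaning. If a 2-week washout was intended, the literal text also lets in the patients the washout was meant to hold back.

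**Working it through.** The plan gives no figure to reproduce, so the check is a day count.

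**Inputs.** Let d be the days from palliative bone radiotherapy to first dose, with 2 weeks = 14 days and 4 weeks = 28 days. Section 6.1.1 requires eligibility to hold on C1D1, so d is counted to that day.

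**Step 1: exclusion 28 alone, as printed.** Barred if d ≤ 28 and not d ≤ 14.

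- d = 1 to 14: admitted
- d = 15 to 28: barred (14 days)
- d ≥ 29: admitted

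Other radiotherapy is barred for d = 1 to 28.

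**Step 2: compare with the two plausible intents over d = 1 to 28.**

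| Intent | Should admit | Wrongly barred | Wrongly admitted | Days wrong |
|---|---|---|---|---|
| A: 2-week washout | 15 to 28 | 15 to 28 (14) | 1 to 14 (14) | 28 of 28 |
| B: recent palliative treatment tolerated | 1 to 28 | 15 to 28 (14) | none | 14 of 28 |

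Days -15 to -28 are wrongly barred under both. Early admission is an error only under A.

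**Step 3: size of the literal effect.** A barred patient becomes admissible at d = 29, so the wait is 29 − d: 29 − 15 = 14 days at most, 29 − 28 = 1 day at least, and 29 − 21 = 8 days for someone irradiated three weeks ago. A patient admissible at d = 14 whose start slips by one day falls into the barred band.

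**Step 4: does the context suggest a slip?** Exclusions 24 to 32 contain eight windows written with ≤. Seven mark a barred period:

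- 24 ("Patients who have been treated with any hematopoietic colony-stimulating growth factors")
- 25
- 26
- the main clause of 28
- 29 (≤ "2 weeks prior to starting study treatment or who have not recovered from side effects of such surgery")
- two in 32 ("Patients who have received investigational agents within" five half-lives, or 4 weeks if the half-life is unknown)

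The note in 28 is the only one that marks an allowed period. The timed allowance in exclusion 24, for erythropoietin or darbepoetin, is written as a minimum of 2 weeks.

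**Step 5: reach of exclusion 25.** If 25 covered radiotherapy, palliative bone treatment would be barred for all of d = 1 to 28. The 4-week window in 28 would then be redundant and its note void. For targeted small molecules, 26 alone bars d = 1 to 14; adding 25 literally bars d = 1 to 28, so the window in 26 would decide nothing and the band in dispute is 28 − 14 = 14 days.

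**Step 6: candidate corrections to the note, with 25 not governing radiotherapy.**

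- Sign changed to >: bars d = 1 to 14. Wrong on 0 days under A, 14 under B.
- Sign changed to ≥: bars d = 1 to 13.
- Window deleted: bars no days. Wrong on 0 days under B, 14 under A.

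**The case against.** **A sensible reader would not apply the bar.** The note relaxes a 4-week rule, so if treatment one week ago is allowed, treatment three weeks ago must be too. That is a reasonable guess at intent B, but it departs from the words, and a site guessing intent A would do the opposite for the first 14 days.

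**The whole point rests on one sign in machine-read text.** Signs are visibly damaged elsewhere: the FGF23 limit in the protocol summary differs from the one in Table 3-1, and the 'promising' range in Section 10.4.3 has an equals sign where an inequality belongs. Neither case shows a > turned into ≤, and Section 5.3 keeps its four inequality signs distinct. The doubt justifies checking the PDF; it does not remove the point.

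**The consequence is small.** This stands. A reader might infer that a patient irradiated three weeks ago is simply refused. The documents do not support that: the window runs to first dose, screening may take up to 28 days, and Section 7.1.1 allows re-screening of patients who do not start. Early dosing is tempered by the recovery requirement in 28, the marrow limits in inclusion 13, investigator judgment under exclusion 23, the C1D1 recheck, and sponsor confirmation of eligibility in the protocol summary. SAP Section 2 reports that most subjects had already stopped treatment, so few future patients may benefit.

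**Exclusion 25 may override the note.** A reader might infer this from Section 6.4.3.1, which lists radiation under anticancer therapy. That section concerns treatment during the study and qualifies radiation by a share of marrow reserve above 30%. Separate windows in 26, 28 and 29 point to specific rules governing their own modality. The same reasoning already resolves 25 against 26, so that overlap needs only a cross-reference.

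**Conclusion.** Exclusion 28 is wrong as written, at low severity. Read literally it bars 14 days (-15 to -28) that neither plausible intent would bar, at the cost of a delay of 1 to 14 days before dosing. If a 2-week washout was meant, it also admits 14 days (-1 to -14) too early, within the safeguards listed above.

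This assumes that the source PDF prints ≤ in the note; if it prints > or ≥, the point falls. It also assumes that exclusion 28, not 25, governs radiotherapy. The documents do not show which intent is right or how many patients are affected. Nothing in the sample size, interim rules or analysis depends on it.

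**What to change.** Check the sign in the source PDF, then have the sponsor confirm the intent, since the wrong choice leaves 14 of 28 days wrong.

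- **If a 2-week washout was meant:** change ≤ to > in the note, so that palliative bone radiotherapy is allowed when given more than 2 weeks before study drug.
- **If recent palliative radiotherapy is tolerated:** delete the 2-week window from the note.
- **In both cases:** keep the recovery requirement, and state in exclusion 25 that radiotherapy is governed by exclusion 28. The 4-week rule for metastatic CNS tumors in exclusion 3 stays.
- **Minor:** add to exclusion 25 that targeted small molecules are governed by exclusion 26.

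The cost is one sign or phrase, two short cross-references and the matching eligibility checklist lines, made by amendment. No procedure, sample size or analysis changes.
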